Safety and Efficacy of Donepezil in Mild to Moderate Alzheimer's Disease: A Multi-center

Single-arm Study in China

NCT02787746

September 18, 2016

Statistical Analysis Plan (SAP)

Safety analysis is conducted on the safety set (SS, patients who receive at least one dose of donepezil 10mg/day and have at least one safety evaluation). Efficacy analysis is conducted on the per protocol analysis set (PPS, patients who complete the study with no major protocol violations) with last observation carried forward (LOCF) as well as the full analysis set (FAS, all enrolled patients are included) LOCF. In addition, in order to test the robustness and accuracy of our results, efficacy analysis is further conducted on the PPS and FAS wherein missing data is not filled in and not included and thus only actual data of every patient who take the efficacy test are included (FAS [actual number] and PPS [actual number], respectively).

For the safety analysis, overall incidence of AEs and SAEs, incidence of AEs and SAEs by organ systems, severity, and AEs' relationship to donepezil are calculated and/or assessed by calculating the number of patients having AEs and SAEs, the prevalence of AEs and SAEs and their 95% confidence intervals (95% CI). Laboratory abnormalities such as changes in alanine aminotransferase (ALT) and aspartate aminotransferase (AST), and changes in EKG and ECG such as HR, QT, QTc are summarized and described using means, standard deviation (SD), median, maximal, minimal, 25th and 75th percentile values, and further analyzed with paired *t*-test. Correlations of AEs and various risk factors are first assessed with univariate logistic regression analysis, and variables included patients' medical history (history of neurological, cardiovascular, mental, liver and gastrointestinal diseases), age (grouped into ≤ 75 and > 75 years), gender, body weight (≤ 55 kg and > 55 kg), APOE genotype ($\epsilon 2/\epsilon 2$, $\epsilon 3/\epsilon 3$, $\epsilon 4/\epsilon 4$, $\epsilon 2/\epsilon 3$, $\epsilon 2/\epsilon 4$, and $\epsilon 3/\epsilon 4$), the presence or absence of APOE $\epsilon 4/\epsilon 4$, concomitant medications (cardiovascular and cerebrovascular, gastrointestinal, liver, neurological, mental and hypoglycemic medications), and duration of donepezil 5mg/day treatment prior to the study (days). Forward stepwise multivariate logistic regression analysis is subsequently performed to

further assess correlations between various risk factors and incidence of AEs using variables chosen from those used in the univariate analysis (SLSTAY=0.3, a significance value of 0.3 is required for a variable to stay in the multivariate model).

MMSE and ADCS-ADL are assessed at each visit. Their changes at each visit from baseline are calculated. Factors affecting MMSE and ADCS-ADL changes are assessed with a mixed model-repeated measures using an autoregressive covariance structure. Variables are the same as those used in the univariate analysis of correlations between AEs and various risk factors

All analyses are performed with SAS 9.4 (SAS Institute Inc.; Cary, NC, USA), data is analyzed with a two-tailed hypothesis, and a *p* value < 0.05 is considered to indicate statistical significance.

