1.3 Analysis Populations

Full Analysis Set (FAS) refers to the ideal subject set as close as possible to the principle of intention analysis (the main analysis includes all randomized subjects). The data set is obtained by excluding all randomized subjects with the smallest and reasonable method. For the estimation of the missing values of the main variables, the last carry-forward obsevation (LOCF) was used to the point where the test data was missing, and the number of subjects who evaluated the efficacy at the end point of each group was consistent with that at the beginning of the test .

Per-Protocol Set (PPS) is composed of all cases that meet the test protocol, have good compliance (the actual dose takes 80% to 120% of the applied dose), do not take prohibited drugs during the test, and complete the contents specified in CRF.

Safety Analysis Set (SAS) is composed of all cases taking drugs at least once and having safety evaluation at least once.

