1.6 Statistical Methods

Complete details of efficacy and safety analyses will be provided in a separate Statistical Analysis Plan (SAP).

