1.7 Efficacy Analysis

1. Primary indicators analysis

For the incidence of adverse events, list the number of subjects with adverse events, and calculate the incidence and confidence interval, and at the same time list the number of various adverse events and their incidence and confidence interval.

2. Secondary indicators analysis

The analysis of the loss rate caused by adverse events is the same as the adverse events.

For the changes in MMSE and ADL scores, list the mean, median, standard deviation, maximum, minimum, 25%, and 75% quantiles. The paired t-test should be carried out for the scores before and after treatment to obtain 95% confidence interval of the changes before and after treatment.

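### FAS-LOCF enters week-4 MMSE and ADL scores as week-20 scores and leaves patients with no post-baseline score undefined; an observed-case week-20 mean or paired t-test cannot reliably check it

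*SAP*

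**What the plan says.** Protocol section 1.4 makes the baseline-to-week-20 changes in MMSE and ADL secondary endpoints. The synopsis (Procedures) schedules both scales at baseline, at Visit 2 after four weeks on 10 mg, and at Visit 3 at week 20. The SAP likewise has them scored at every visit.

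The SAP's first paragraph runs efficacy on the PPS (completers without major violations) with LOCF and, alongside it, on the "full analysis set (FAS, all enrolled patients are included) LOCF". It then adds runs on both sets, "in order to test the robustness and accuracy of our results", in which "missing data is not filled in and not included".

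Protocol section 1.3 also describes LOCF. It introduces the rule with "For the estimation of the missing values of the main variables" and says that "the number of subjects who evaluated the efficacy at the end point of each group was consistent with that at the beginning" of the test. The same section builds the FAS by "excluding all randomized subjects with the smallest and reasonable method", which appears to allow a minimum of exclusions.

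On the method, Protocol section 1.7 says: "The paired t-test should be carried out for the scores before and after treatment", with a 95% CI for the change. It names no analysis set. Section 1.6 defers the detail to the SAP. The SAP's paragraph on MMSE and ADCS-ADL plans a repeated-measures mixed model with autoregressive covariance, but only for factors that affect the changes.

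**The concern.** A patient who leaves after Visit 2 contributes a score up to 16 weeks early to a week-20 endpoint. If the mean course moves between weeks 4 and 20, the reported change is off. Filled-in values also count as observed ones, so the interval is usually narrower than the week-20 data support.

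A patient who leaves before Visit 2 has nothing to carry forward except baseline. Keeping all enrolled patients (SAP) and the protocol's equal-number sentence both point to entering such a patient as zero change. The exclusions in section 1.3, and its limit to main variables, point the other way. The two rules give different estimates.

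The planned safeguard is the comparison with unfilled data. A week-20 observed-case mean ignores the week-4 scores of those who left. If leaving depended on those scores, the check is biased too, and agreement or disagreement with LOCF settles little. At stake are the reported size and CI of the trial's efficacy results.

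**Working it through.** **Inputs from the documents.** N = 554 and 20% dropout (Protocol section 1.1), with scores at baseline, week 4 and week 20 only. The planned size reproduces: an exact (Clopper-Pearson) 95% interval of width 0.08 at 76% needs 461 patients, and 461 × 1.20 = 553.2, rounded up to 554. Only N and the dropout rate are used below. At 20%, 0.20 × 554 = 110.8, so about 111 patients could lack a week-20 score.

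**Assumed, because the documents give none.** Mean changes D4 and D20, their SDs, their correlation, the timing of dropout (p1 before week 4, p2 after) and how dropout depends on scores. The scale is MMSE-like; ADL would need its own values.

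**LOCF bias when dropout is unrelated to scores.**
- Zero-fill (no post-baseline score enters as 0): mean = (1 − p1 − p2) × D20 + p2 × D4, so bias = p2 × (D4 − D20) − p1 × D20.
- Exclusion (such patients left out): the same mean divided by (1 − p1), so bias = [p2/(1 − p1)] × (D4 − D20).

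The first part is the carried-forward fraction times the week-4 minus week-20 difference. Zero-fill adds shrinkage toward zero.

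Linear course, D4 = 0.2 × D20; share of the change lost:

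| p1, p2 | Zero-fill | Exclusion |
|---|---|---|
| 0.2, 0 | 20% | 0% |
| 0.1, 0.1 | 18% | 8.9% |
| 0, 0.2 | 16% | 16% |

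Non-linear course, D4 = +1.0 and D20 = +0.3, with p1 = p2 = 0.1: zero-fill gives 0.8 × 0.3 + 0.1 × 1.0 = 0.34, and exclusion gives 0.34/0.9 = 0.38. Both overestimate. The direction depends on the course.

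**Standard error.** LOCF SE divided by observed-case SE, for assumed week-4/week-20 SDs of 2.5/3.5, 3.5/3.5 and 3.5/2.5:
- half leaving before week 4: zero-fill 0.83, 0.85, 0.90; exclusion 0.92, 0.94, 1.00;
- all leaving after week 4 (both rules coincide): 0.85, 0.90, 0.98.

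Over these cases the LOCF SE is 2% to 17% smaller under zero-fill and 0% to 15% smaller under exclusion.

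**Coverage, random dropout, p1 = p2 = 0.1, SDs 2.5/3.5.** The nominal SE is about 0.138 (zero-fill) or 0.153 (exclusion). With r = bias/SE, coverage is approximately Φ(1.96 − r) − Φ(−1.96 − r).

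| D4, D20 | Zero-fill | Exclusion |
|---|---|---|
| −0.2, −1.0 | bias 0.18, r = 1.30, 75% | bias 0.089, r = 0.58, 91% |
| −0.1, −0.5 | bias 0.09, r = 0.65, 90% | bias 0.044, r = 0.29, 94% |
| +1.0, +0.3 | bias 0.04, r = 0.29, about 94% | bias 0.078, r = 0.51, 92% |

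Simulation agrees with these. In the first row, observed cases and the likelihood model both average −1.00 with 95% coverage.

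**Dropout that depends on scores.** Simulation with n = 554, true change −0.2 then −1.0, SDs 2.5/3.5, correlation 0.6 and a logistic slope of −1 per SD of week-4 change. Observed cases here means the week-20 mean with a t interval. The likelihood model is an unstructured bivariate normal fit to the observed week-4 and week-20 changes. Cells show mean and coverage.

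| Analysis | 10% early at random, 10% late on week-4 score | All 20% late on week-4 score |
|---|---|---|
| LOCF, zero-fill | −0.85, 80% | −0.89, 88% |
| LOCF, exclusion | −0.94, 94% | −0.89, 88% |
| Observed cases | −0.79, 75% | −0.63, 40% |
| Likelihood model | −1.00, 95% | −1.00, 95% |

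If early dropout also depends on the unseen week-4 score, coverage is 32% (zero-fill), 61% (exclusion), 34% (observed cases) and 78% (likelihood model, mean −0.81).

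**The case against.** The strongest reply concerns the method. The SAP does not say how its unfilled runs are analysed, and the only inferential method it gives for MMSE and ADL is the mixed model. On unfilled FAS data, that model keeps the week-4 scores of later dropouts, so the bias shown for observed cases need not arise. A reader might infer that the observed-case checks are biased as planned. The documents do not support that: the bias attaches to a week-20 mean or to the protocol's paired t-test. What stands is that the SAP assigns the mixed model to factors, not to the mean week-20 change, and that the paired t-test is the only method stated for that change. Applying it to the SAP's sets means joining the two documents.

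A reader might also infer that no analysis takes precedence. That is too strong, because the SAP presents the unfilled runs as additional checks and so puts LOCF first. Section 1.3 also has a parenthesis about the main analysis, but it explains the intention-to-treat principle in terms of randomised subjects, in a trial with no randomisation, and designates no set for MMSE or ADL. The gap that remains is FAS-LOCF against PPS-LOCF. PPS patients complete the study, so LOCF matters mainly in the FAS.

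The size is also open to challenge. The 75% figure belongs to one assumed true change, and the other random-dropout cases give 90% to 94%. The biases there are at most 0.18 points against an assumed SD of 3.5. All of this stands, as does the point that a gap between LOCF and unfilled results would be visible if both are reported. Seeing a gap, however, does not show which result is nearer the truth.

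**Conclusion.** The point holds in a limited form. That FAS-LOCF enters week-4 scores as week-20 scores follows directly from the visit schedule. The handling of patients with no post-baseline score is unresolved between SAP and protocol; zero change is the more natural reading but is an inference. FAS-LOCF and PPS-LOCF are unranked. The observed-case run cannot reliably check LOCF if it is a week-20 mean or paired t-test and dropout depends on the week-4 score.

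Neither size nor direction can be derived from the documents. With random dropout and half leaving before week 4, LOCF coverage in the assumed examples runs from 75% to about 94%; at the upper end the harm is negligible. Nothing supports a claim that LOCF systematically flatters the drug, since the examples err both ways.

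A reader might carry this over to the trial's main result. That would be wrong: the primary AE incidence is untouched, and the plan sets no success threshold for MMSE or ADL. The effect is on the reported size and CI of secondary endpoints. The change is worth making because it is cheap. Confidence is medium.

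**What to change.** In the SAP, make the main week-20 estimate and 95% CI for MMSE and for ADL come from a likelihood-based repeated-measures model on observed week-4 and week-20 changes in the FAS, without LOCF, with categorical visit, baseline score and unstructured covariance. With two post-baseline visits, unstructured covariance costs little (two variances and one covariance) and does not force equal variances. State the missing-at-random assumption and report how many patients have no post-baseline score. Keep the LOCF and observed-case analyses as sensitivity analyses. For LOCF, state how patients with no post-baseline score are treated, so that Protocol section 1.3 and the SAP agree.

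The cost is SAP wording and a few lines of SAS code on data already collected; a repeated-measures model is already planned for the factors analysis. The limits should be stated too. The estimate relies on missing at random. If dropout is random it gains almost nothing over observed cases (SE 0.163 against 0.166). It also does not cure dropout that depends on unseen scores, as the 78% coverage above shows.

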ELIGIBILITY CRITERIA	
Inclusion Criteria:
 
 1. Patients between 50 and 85 years of age. 2. Patients newly diagnosed as probable AD based on Diagnostic and Statistical Manual of Mental Disorders, 4th Edition, Text Revision (DSM-IV-TR) criteria and National Institute of Neurologic and Communicative Disorders and Stroke—AD and Related Disorders Association (NINCDS-ADRDA) criteria; Mild to moderate AD with Mini-Mental State Examination (MMSE) 10-24, modified Hachinski ischaemic scale (MHIS)≤4, Activity of daily life scale (ADL)≥23, and Hamilton Depression Scale (HAMD) <7. 3. MRI image supports the diagnosis of AD (medial temporal lobe atrophy, Fazekas scale of white matter lesions≤2 within 6 months prior to the screening). 4. 5mg daily of Donepezil for at least four weeks before the screening. 5. Patient with exclusive caregiver. 6. Patient should be ambulatory or ambulatory aided by a walker or cane. 7. With good eyesight and hearing, can cooperate with the examination and treatment. 
Exclusion Criteria:
 
 1. Patients with vascular dementia, other types of dementia or with other psychiatric or neurological disorders (e.g. delirium, depression, Parkinson's disease, etc.). 2. Patients with type I diabetes, obstructive lung disease or asthma, vitamin B₁₂ or folic acid deficiency, thyroid dysfunction, severe liver or kidney dysfunction, severe cardiac insufficiency (congestive heart failure, myocardial infarction, sick sinus syndrome, II-III degree atrioventricular block or heart rate<50 beats/minute [bpm]). 3. Epilepsy or head trauma resulting in unconsciousness that occurred in the two years prior to the screening. 4. Patients with hematologic diseases (such as anemia, granulocytes, leukemia, etc.), tumor, neoplasms within 2 years prior to the screening. 5. Patients with a history of alcohol dependence and drug abuse. 6. Patients with known hypersensitivity to medicines or
----------------------	---

	
foods;
 
 7. Patients taking anticholinergic agents or antihistaminic agents; 8. Patients who had been hospitalized continuously for more than 3 months before the screening.

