	
Visit 2 (maintain 10mg dose within 7 days after 4 weeks)
 
1. Check whether the subjects take the medicine strictly according to the clinical trial plan.2. Vital signs measurement.3. MMSE score, ADL score.4. APOE genotyping test.5. Blood biochemical examination.6. ECG examination.7. Record adverse events.8. Record combined medication.9. Instruct the subjects to follow up after being enrolled for 20 weeks. If the subjects have any questions or abnormal conditions during this period, they can contact the researchers at any time. 
Visit 3 (maintain 10 mg dose for 20 weeks ± 7 d)
 
1. Check whether the subjects take the medicine strictly according to the clinical trial plan.2. Vital signs measurement.3. MMSE score, ADL score.4. Laboratory inspection.5. ECG examination.6. Record adverse events.7. Record combined medication.
--	--

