1.8 Other Safety Data Analysis

For the QT interval and heart rate before and after treatment, the mean, median, standard deviation, maximum, minimum, 25%, 75% quantiles were used for statistical description, and the scores before and after treatment were paired t-tested. At the same time, the 95% confidence interval of the change value before and after treatment is obtained. Based on the predetermined MCID value, the 95% confidence interval is compared with the lower limit of the 95% confidence interval to determine whether the changes in QT interval and heart rate have clinical significance.

For vital signs, the mean, median, standard deviation, maximum, minimum, and 95% confidence intervals were used to describe the changes in vital signs at each follow-up point.

For laboratory examination and ECG, the clinical significance judgment and frequency (or frequency) of all indexes before and after treatment are made in a cross table, and the details of abnormal examination items after treatment are listed.

For quantitative laboratory test values, list the mean, median, standard deviation, maximum, minimum, 25%, 75% quantiles, and paired t-test for the scores before and after treatment to obtain 95% confidence interval of the changed value to evaluate its safety.

● **Adverse Events**

When filling out the adverse event form, the researcher should use mild, moderate, and severe to describe the intensity of the adverse event. To unify the standard, the classification of event intensity is as follows:

Moderate: To some extent affects the normal function of the subject.

Severe: Obviously affect the normal function of the subject.

- Mild: Does not affect the normal function of the subject.
- Moderate: To some extent affects the normal function of the subject.
- Severe: Obviously affect the normal function of the subject.

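### Laboratory and ECG safety is formally tested only on mean change, and the protocol's patient-level tables lack limits, a visit rule, confidence intervals and a place in the SAP

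*SAP*

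**What the plan says.** **SAP, safety analysis.** Adverse events and serious adverse events get patient counts with 95% confidence intervals. ALT and AST changes and ECG measures do not: "changes in EKG and ECG such as HR, QT, QTc are summarized and described using means, standard deviation (SD), median, maximal, minimal", then "25th and 75th percentile values, and further analyzed with paired *t*-test". The SAP gives no limit, no count of patients beyond a limit and no cross table for these measures.

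**Protocol 1.8.** QT interval and heart rate are described by summary statistics and a paired t-test. The confidence interval of the mean change is then used "to determine whether the changes in QT interval and heart rate have clinical significance". The benchmark reads: "Based on the predetermined MCID value, the 95% confidence interval is compared with the lower limit of the 95% confidence interval". No MCID value is given, and as worded the interval is compared with its own lower limit. Quantitative laboratory values also get a paired t-test.

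The same section plans two patient-level outputs for laboratory tests and ECG. One is a table: "the clinical significance judgment and frequency (or frequency) of all indexes before and after treatment are made in a cross table". The other is a listing: "the details of abnormal examination items after treatment are listed".

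**Protocol, Procedures.** Biochemistry and ECG are done at Visit 2 (after 4 weeks on 10 mg), and laboratory tests and ECG at Visit 3 (20 weeks). Extra safety visits are allowed at any time. There are therefore at least two on-treatment measurements per completer.

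**Protocol 1.6** defers the full detail of the safety analyses to the SAP.

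**The concern.** The primary endpoint of this trial is safety. For ECG and liver tests the safety question is how many patients reached a worrying value, and a mean change says only whether the average patient moved. If a few per cent of patients have a marked change and the rest none, the mean stays near zero, its interval can include zero, and 1.8 would then support a conclusion of no clinically significant change.

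The cross table and listing are the natural safeguard, but as written they cannot be programmed or reproduced:

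- The criteria for clinical significance and for abnormality are not stated.
- The comparison is before versus after treatment, although two scheduled visits and any unscheduled ones fall on treatment. A value that is abnormal at Visit 2 and normal at Visit 3 could be classified either way.
- A listing has no denominator or rate, and no confidence interval is planned for the cross table.
- Neither output appears in the SAP, the document to which 1.6 refers the reader.

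**Working it through.** **The plan's own figure.** The documents give no figure for laboratory or ECG outliers, so the sample size is used only to set n. For an expected incidence of 76% and a full interval width of 8%, the smallest n by the exact (Clopper-Pearson) method is 461, where the width is 0.07996. This reproduces the plan. The enrolled number is 461 × 1.2 = 553.2, rounded up to 554.

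**Assumed inputs (none is in the documents).** A number k of n = 461 patients have a 20 bpm fall in heart rate and the others have no true change. Each patient's change carries normal noise with SD σ = 8 bpm, varied from 6 to 12.

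**Mean and t-test.** With f = k/n:

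- mean = −20f
- SD of change s = √(σ² + f(1 − f) × 20²)
- SE = s/√n
- power from the noncentral t with 460 df, noncentrality mean/SE, two-sided 5%

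For k = 14 and σ = 8:

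- mean = −280/461 = −0.61
- s = √(64 + 0.0304 × 0.9696 × 400) = 8.7
- SE = 8.7/21.47 = 0.405
- 95% CI = −1.40 to 0.19
- noncentrality = −1.50, power about 32%

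| Affected (k) | Mean change | Power, σ = 6 | Power, σ = 8 | Power, σ = 12 |
|---|---|---|---|---|
| 14 (3.0%) | −0.61 | 47% | 32% | 18% |
| 23 (5.0%) | −1.00 | 82% | 65% | 39% |
| 28 (6.1%) | −1.21 | 92% | 80% | 52% |

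**A second example, for QT (also assumed).** If 5 of 461 patients have a 60 ms increase, the mean moves by 5 × 60/461 = 0.65 ms. With an SD of 15 to 25 ms, simulation gives significance in about 12% down to 7% of trials, little above the 5% false-positive rate.

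**The count, under the same noise.** It would be unfair to give noise to the t-test and none to the count. With k = 14, σ = 8 and a category of falls of 20 bpm or more at one visit:

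- affected patients flagged: 14 × 0.5 = 7
- unaffected patients flagged: 447 × P(Z < −2.5) = 447 × 0.0062 = 2.8
- total: about 10 of 461 (2.2%), exact 95% CI 1.0% to 4.0%, with about 2.8/9.8 = 28% of those flagged being unaffected

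So the count does not return the true 3.0% (14/461, exact interval 1.7% to 5.0%). It does put the extreme patients in the report with a rate and an interval, which the mean does not.

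**The cost of taking the worst value.** With two on-treatment visits, the expected number of unaffected patients flagged is at most 2 × 2.8 = 5.6. It would be lower to the extent that the two changes share a baseline and are correlated.

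**The case against.** The strongest reply is that the plan is not confined to means. Protocol 1.8 has a cross table for all laboratory and ECG indexes and a listing of abnormal results. Both documents report minima and maxima, and adverse events are counted by patient with intervals. The protocol synopsis is dated 9 October 2016, after the SAP of 18 September 2016, and nothing in the SAP withdraws the table or listing. All of this stands. A reader might infer that the plan cannot show harm in a few patients, and the documents do not support that.

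Three other inferences also go too far:

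- **That the judgment is made by an unblinded investigator.** The trial is open-label, but 1.8 does not say who judges clinical significance.
- **That a Visit 2 abnormality will be missed.** The text does not say which visit is used, and it does not exclude Visit 2.
- **That a heart rate below 50 bpm is the protocol's on-treatment safety limit.** It is an entry exclusion, listed under severe cardiac insufficiency.

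It is also fair to say that the size depends on assumptions. At 28 affected patients and SD 8, the t-test has 80% power.

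The reply does not supply the missing criteria, visit rule or rates. A minimum or maximum shows one patient at each end, not how many crossed a limit. The documents do not say that an abnormal laboratory or ECG value must be recorded as an adverse event, so the adverse-event counts are only partial cover. A significant t-test would still not say how many patients were affected.

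**Conclusion.** The concern holds in a limited form. The only formal tests of laboratory and ECG change are on before-after means, and 1.8 bases its conclusion on QT and heart rate on the interval of the mean. That statistic has low power when a small share of patients changes markedly: about 32% at 3.0% affected and 65% at 5.0%, for a 20 bpm fall with SD 8. Those rates, shifts and SDs are illustrations, and other values would move the figures. That a mean cannot report how many patients were affected does not depend on them.

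The patient-level outputs exist in the protocol but are underspecified and absent from the SAP. The adverse-event incidence, which is the primary analysis, is not affected.

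**What to change.** In protocol 1.8 and the SAP:

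1. Alongside the means, report the number and percentage of safety-set patients, with exact 95% confidence intervals, whose worst value at Visit 2, Visit 3 or an unscheduled visit crosses a reporting limit. Fix limits for heart rate, QTc, QTc increase, ALT and AST before database lock. Heart rate below 50 bpm, already used at entry, can serve as a reporting category only. These are categories for tables, not rules for managing patients.
2. Build the existing cross tables from baseline to worst on-treatment value, state the criteria and who applies them, and carry the tables and the listing into the SAP.
3. State the QT correction formula. Give the MCID value and reword the comparison in 1.8.
4. Do not draw the clinical-significance conclusion for QT and heart rate from the interval of the mean alone.

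**Cost.** This needs SAP and protocol wording and a few programmed tables, with no new visits or measurements. The real downside is that taking the worst of several visits against one baseline, without a control arm, raises crossings through ordinary variability. Reporting the proportion beyond each limit at baseline and the counts at each visit lets the reader judge how much of the excess that explains.

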DRUG DOSAGE AND FORMULATION	Once a day, two tablets at a time. Take it orally before bed at night (insomniacs can take it after breakfast). If the subject cannot tolerate 10 mg, he can return to the 5 mg dose, and after 4 weeks of use, increase the dose to 10 mg for the second time. If the second dose is increased to 10 mg and can not tolerate, the person who returns 5 mg or discontinues the drug is considered to be discontinued.
ROUTE OF ADMINISTRATION	Oral
TREATMENT DURATION	Use 10mg dose for 20 weeks.

PROCEDURES	
Subjects conducted 3 visits at baseline (-5 to 0 days), maintained 10mg dose within 7 days after 4 weeks and maintained 10mg dose for 20 weeks \pm7 days, during which the follow-ups of subjects can be increase at any time with safety of drug .
 
Visit 1 baseline (- 5 to 0 days)
 
 1. The purpose of this visit is to examine whether the subjects are suitable for the study. 2. The subjects and their guardians sign the informed consent form after understanding the research. 3. General information collection: fill in demographic data, inquire about allergy history, inquire about past diseases, record combined diseases and medication, etc. 4. Vital signs measurement. 5. MMSE score, MIS score, ADL score, HAMD score. 6. Laboratory inspection. 7. Syphilis, folic acid and vitamin B12 examination, thyroid function T3, T4 examination. 8. Head MRI (head MRI should include axial position and coronal position. Previous head MRI with diagnostic reference value can be exempted from this item, but it should have detailed image description). 9. ECG examination. 10. Record adverse events. 11. Record combined medication. 12. Inform the subjects to follow up within 7 days after maintaining the dose of 10mg for 4 weeks. If the subjects have any questions or abnormal conditions during this period, they can contact the researchers at any time.
-------------------	---

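### The AE risk-factor models leave out baseline disease severity, although MMSE is scored at Visit 1, so a severity effect cannot be found and could be partly credited to other factors

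*SAP*

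**What the plan says.** The AE risk-factor analysis is described only in the SAP, and it has two steps.

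- **Univariate step.** "Correlations of AEs and various risk factors are first assessed with univariate logistic regression analysis". The candidates begin with "variables included patients' medical history (history of neurological, cardiovascular, mental, liver and gastrointestinal diseases") and continue with age (cut at 75 years), gender, body weight (cut at 55 kg), APOE genotype in six categories, APOE ε4/ε4 yes or no, six classes of concomitant medication, and days on donepezil 5 mg before the study.
- **Multivariable step.** A forward stepwise logistic model follows, "using variables chosen from those used in the univariate analysis". The retention rule is lenient: "a significance value of 0.3 is required for a variable to stay in the multivariate model".

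Neither step includes MMSE, ADL or any other measure of severity. The SAP uses MMSE only as an outcome, through its change from baseline.

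The protocol shows that the value exists. Inclusion criterion 2 requires "Mild to moderate AD with Mini-Mental State Examination (MMSE) 10-24", and item 5 of Visit 1 lists "MMSE score, MIS score, ADL score, HAMD score". The relation between APOE genotype and AEs is a named secondary endpoint (Protocol 1.4), and the SAP's logistic models are its only stated analysis. Neither document explains the omission or plans a severity-adjusted sensitivity analysis.

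**The concern.** An MMSE range of 10 to 24 covers patients who may differ a good deal in frailty, in co-treatment and in how fully their symptoms come to notice. Severity is thus an obvious candidate risk factor for a recorded AE, yet the list tests age, weight and gender and not severity.

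Two things follow. First, if severity does affect AE risk, the planned search cannot find it. Second, if severity also differs between levels of a listed factor, that factor's odds ratio can absorb part of the severity effect. The listed factors are not alike here. Severity could influence concomitant medication and time on 5 mg, so for these it could be a confounder. Age and APOE genotype come before severity, so for these it is better seen as a pathway. In either case a reader of the planned output could not tell how much of an association runs through severity.

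**Working it through.** **1. Can severity enter at any step?** The univariate list has 5 histories, age, gender, weight, APOE (6 genotypes and a separate ε4/ε4 indicator), 6 medication classes and days on 5 mg. The stepwise model is confined to the same variables. MMSE cannot enter either step.

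**2. Is it available?** MMSE is needed to judge eligibility and is scored at Visit 1, so every eligible patient should have a value.

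**3. How large could the effect be?** The plan gives no figure on this point, and the documents hold no data linking MMSE to AEs, age or APOE. What follows is an illustration.

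Inputs from the documents are an expected AE incidence of 76%, 461 evaluable patients and 554 enrolled (Protocol 1.1). As context, 461 is reproduced as the smallest n for an exact 95% interval of full width 8 points at 76%, and 461 × 1.2 = 553.2, rounded up to 554.

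Assumptions are a difference g of 5, 10 or 15 points in AE incidence between moderate and mild patients (lower in moderate), a difference d of 10, 20 or 30 points in the share of moderate patients between two equal groups, and no effect of the grouping factor itself. The groups then differ in AE incidence by g × d, placed symmetrically around 76%.

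| g | d | g × d | Incidences | Odds | Odds ratio |
|---|---|---|---|---|---|
| 0.05 | 0.10 | 0.005 | 0.7625, 0.7575 | 3.211, 3.124 | 0.973 |
| 0.10 | 0.20 | 0.020 | 0.7700, 0.7500 | 3.348, 3.000 | 0.896 |
| 0.15 | 0.30 | 0.045 | 0.7825, 0.7375 | 3.598, 2.810 | 0.781 |

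If AEs rise with severity instead, these become 1/0.973 = 1.03, 1/0.896 = 1.12 and 1/0.781 = 1.28.

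**4. How often would this give p < 0.05?** With n = 277 per group, SE(log OR) = √[1/(277 p₁(1−p₁)) + 1/(277 p₀(1−p₀))], about 0.20. For the middle row, log OR = −0.110 and |log OR|/SE = 0.55, so the probability is Φ(0.55 − 1.96) + Φ(−0.55 − 1.96), about 8.5%. The top row gives about 5% and the bottom row about 24%, against a nominal 5%. If the comparison group holds 15% of patients, the bottom row gives about 14%.

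**5. A second illustration with continuous MMSE.** The assumptions are N = 554, 76% incidence, MMSE with SD 4 before clipping to 10–24, a comparison group 1 to 3 points lower before clipping, and odds of a recorded AE rising by a factor of 1.05 to 1.15 per MMSE point. The group odds ratio runs from 0.96 to 0.69. The chance of p < 0.05 runs from about 6% to 45% with equal groups, and from about 5% to 29% with a 15% group. This range is wider because the assumptions are stronger, and the documents support them no better.

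**6. What does one more term cost?** Non-redundant parameters now: 5 + 1 + 1 + 1 + 5 (genotype) + 6 + 1 = 20. Patients without an AE are the rarer outcome: 554 × 0.24 = 133. Non-events per parameter go from 133/20 = 6.6 to 133/21 = 6.3. With 461 patients, 461 × 0.24 = 110.6, and the ratio goes from 5.5 to 5.3.

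**The case against.** The strongest reply is that nothing here is an error. The models are correlational screening, the SAP claims no causal or severity-independent effect, and the choice of candidates is partly judgement. The secondary endpoint asks for the association between genotype and AEs, and an estimate not adjusted for MMSE answers that. Replacing it with an adjusted one would change the question. This stands, and it is why the remedy below keeps the estimate without MMSE and adds a second one.

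Three stronger readings are tempting, and the documents do not support them.

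- *Severity confounds the APOE endpoint.* Genotype is fixed before the disease begins, so severity is not a common cause of genotype and AEs. It can lie between them. Age also comes first.
- *More impaired patients under-report AEs.* The visit schedules say only that AEs are recorded, not how they are elicited or by whom. The protocol also requires "Patient with exclusive caregiver", which could offset under-reporting. The direction of any distortion is open.
- *The trial fails its title because it does not compare mild with moderate disease.* The title describes who is enrolled. No objective or endpoint compares the two, and no MMSE cut between them is given.

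The reply does not remove the gap itself. A search for AE risk factors that cannot consider the severity score used to select its patients is incomplete, and the value is already collected.

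**Conclusion.** The point holds in a limited form. The candidate list is closed, the stepwise model is bound to it, and baseline severity is absent from both. The planned analysis therefore cannot detect a severity effect on AEs, and part of an association with age, APOE, concomitant medication or prior 5 mg duration could reflect severity.

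Whether it would, in which direction and by how much cannot be learned from the documents. Odds ratios of 0.97 to 0.78 (or 1.03 to 1.28), and 0.96 to 0.69 in the second illustration, rest wholly on assumed inputs. At the mild end the effect is negligible. The large values need a steep severity gradient and a marked imbalance together.

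This is an inexpensive improvement to a secondary, exploratory analysis. A reader might infer that the overall AE rate is biased too, but the primary incidence and its confidence interval use no covariates and are not affected.

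**What to change.** 1. Add Visit 1 MMSE, as a continuous variable, to the univariate candidate list in the SAP. It then also becomes a candidate for the stepwise model.
2. For APOE and for age, report the odds ratio with its 95% CI both without and with baseline MMSE, in the same patients and with the other terms unchanged. In the second column MMSE stays in whatever its p-value.
3. State the reading in advance: the estimate without MMSE is the total association, and the estimate with MMSE is the association not explained by severity. Logistic odds ratios can shift a little when any predictive covariate is added, so a small difference between columns should not be over-read.
4. The SAP reuses the same list for the mixed models of MMSE and ADCS-ADL change, so say whether the addition applies there.

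A table of AE incidence by severity is optional; if wanted, its MMSE cut should be fixed in the SAP before analysis.

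The cost is one degree of freedom and one extra column of estimates, with no new data or visits.
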